likelihood of Type II error due to small sample sizes. Therefore, we will not rely on statistical tests and p-values alone to evaluate HTE; we will rely on estimated effect sizes (estimate divided by the standard deviation) and compute confidence intervals around these effect sizes.

Evaluation of Attrition

We will recruit 600 participants and randomly assign them to two arms with equal allocation (300 per arm). Based on previous experience, we assumed 20% attrition by 12 months. In addition to enhancing the process of full informed consent, these procedures are designed to decrease the likelihood of study attrition due to inadequate appreciation of the time, effort, and component activities involved in participating in the intervention program, or in the study protocol.

Analyses for Primary Study Aims and Hypotheses

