Analysis for Aim 1: All analysis will be conducted on the full sample regardless of exposure to treatment (intent to treat). Our **primary hypothesis** in **Aim 1** is that I-IMR compared to CDSMP will be associated with greater improvements in physical health self-management abilities (Self-Rated Abilities for Health Practices) and physical health consumer activation (Patient Activation Measure). To test this hypothesis, we will fit generalized linear mixed-effects linear models (GLMM) with identity link functions and normal distribution specification. Treatment arm (I-IMR and vs. CDSMP), time (baseline, 4-, 8- and 12-month), and arm-by-time interactions will be specified as fixed effects. Intercept and time will be specified as random effects to take the correlated nature of the data resulting from repeated measures into account. The primary hypothesis of interest will be examined by testing if the arm-by-time interaction effect (difference in rate of improvement over 12 month) is significantly different from zero. Our **secondary hypothesis** is that I-IMR compared to CDSMP will have greater improvement in self-reported **physical health** functioning (PROMIS Global Health Measure). The same GLMM model will be used to test this hypothesis. Qualitative data for Aims 1 and 2 will be audio-recorded, de-identified and transcribed, and analyzed with ATLAS.ti using the “grounded theory” approach.⁸⁵ The Research Support Team will read data and develop operational definitions from transcript coding, a validated approach which allows for multiple perspectives.⁸⁵ Codes will be assigned to text, grouped, and checked for themes. The codebook will consist of *a priori* researcher-driven codes, derived from interviews and inductively derived codes from qualitative data.⁸⁵ Analyses will assess within group consensus or disagreement. Member checking will be employed to validate qualitative results and resolve any incongruent findings.

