Analysis for Aim 2: Our **primary hypothesis for Aim 2 is that** I-IMR compared to CDSMP will be associated with greater improvements in **mental health self-management abilities** (Illness Management and Recovery Scale⁸⁰); and **mental health consumer activation** (Patient-Activation Measure-MH⁸¹); and our **secondary hypothesis** is that I-IMR compared to CDSMP will be associated with greater improvements in self-reported **mental health** functioning (PROMIS Global Health Measure⁷⁹). We will use the same GLMM approach to test primary and secondary hypotheses for Aim 2.

Analysis for Aim 3: We hypothesized that (1) participation in I-IMR compared to CDSMP will result in greater reductions in emergency room (ER) visits and acute care hospital days compared to the 12 months before participation; and (2) greater reduction in 10-year cardiovascular mortality risk (ACC/AHA Cardiovascular Risk Score⁸²) over 12 months. To test **Aim 3** (1), we will compute the total number of ER visits and hospital days 12-months before intervention, and 12-months after intervention, and fit the same generalized linear mixed model (GLMM) but with log link function and Poisson, or negative binomial or zero-inflated distribution (depending on model fit) because the

outcomes are counts and are likely to be skewed with a cluster of zero values.⁸⁶ The arm, time (before vs. after) and arm*time interaction will be included as fixed effects, and the superiority hypothesis of I-IMR compared to CDSMP will be tested with the significance of the interaction term. For this analysis, because we cannot ensure covariates are balanced between two arms 12-months before randomization, we will test group (arm) balance with respect to demographic and clinical covariates. Depending on the number of imbalances we find, we will either include covariates in the model or use propensity score adjustment with inverse probability weighting to balance the groups.

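### Aim 3 (1): the hospital-day superiority test depends heavily on which permitted count family is fitted, and the family that fit is likely to favour does not test the change in total days

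*Combined protocol and SAP*

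**What the plan says.** The Aim 3 paragraph of section 4 (Analysis) in the combined protocol and SAP sets up the data as follows: "we will compute the total number of ER visits and hospital days 12-months before intervention, and 12-months after intervention". The model is the one used for Aim 1, now "with log link function and Poisson, or negative binomial or zero-inflated distribution (depending on model fit"). The reason given is that the "outcomes are counts and are likely to be skewed with a cluster of zero values". The decision rule is that "the superiority hypothesis of I-IMR compared to CDSMP will be tested with the significance of the interaction term".

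The random effects carry over from the Aim 1 paragraph: "Intercept and time will be specified as random effects to take the correlated nature of the data". If the arms look unbalanced, the plan may add covariates or "use propensity score adjustment with inverse probability weighting to balance the groups".

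The plan does not say which fit criterion applies, whether both outcomes must share a family, or which part of a zero-inflated model holds the tested interaction. It also does not say how the standard error is computed. No sandwich, bootstrap or randomisation-based inference is mentioned.

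**The concern.** Zeros and skew are only part of the problem. A participant's hospital days are a small number of admissions, each contributing a run of days of variable length. The three permitted families handle this differently:

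- Poisson treats each day as a separate event.
- The negative binomial has variance mu + mu^2/k, so one parameter must serve both the many zeros and the long stays.
- A zero-inflated model splits the mean in two, and the count-part interaction describes only one of the two pieces.

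Choosing the family by fit fixes neither the size of the standard error nor the quantity being tested. At stake is a stated superiority hypothesis. The p-value could turn on a modelling choice, and the reported coefficient might not be the reduction in hospital days that Hypothesis 3 is about.

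**Working it through.** **1. The plan's own figure.** It will "randomly assign them to two arms with equal allocation (300 per arm") and expects 20% loss: 600 x (1 - 0.20) = 480, as stated in section 9b. This gives 240 per arm. No event rate, stay length, dispersion, effect size or power is given for Aim 3.

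**2. Assumed inputs (none from the documents).**
- Hospital days: 0.3-1.0 admissions a year, stay scale or median about 5-7 days, and gamma or log-normal differences between people.
- ER visits: mean 2.0-2.3 a year.
- Test: two-sided 5%, which the plan states only for the COVID component.
- Models: random intercept only, Hessian-based errors.

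**3. Why Poisson fails for days.** If a person's admissions are Poisson, the variance-to-mean ratio of total days is E(L^2)/E(L), where L is the length of stay. For a log-normal stay with median 5.5 and log-SD 0.9, this is 5.5 x exp(1.5 x 0.81) = 5.5 x 3.37 = 18.5. Poisson assumes 1. The expected SE/SD is about 1/sqrt(18.5) = 0.23.

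**4. Simulation with no treatment effect.** There were three scenarios per outcome and 300 runs each. Monte Carlo error at 5% is sqrt(0.05 x 0.95/300) = 1.3 points. SE/SD is the mean standard error divided by the empirical SD of the interaction estimate.

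| Analysis | Days: SE/SD | Days: type I | ER: SE/SD | ER: type I |
|---|---|---|---|---|
| Poisson | 0.20-0.30 | 61-69% | 0.39-0.65 | 20-44% |
| Zero-inflated Poisson | 0.21-0.35 | 55-74% | 0.41-0.66 | 18-44% |
| Negative binomial | 1.28-1.41 | 0.3-1.0% | 0.92-1.11 | 3.0-9.0% |
| Zero-inflated negative binomial | 0.87-1.03 | 4.0-9.0% | 0.92-1.09 | 3.7-9.3% |
| Log-link mean model, participant sandwich | 0.95-1.03 | 3.0-6.7% | 0.90-1.10 | 2.7-9.0% |

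Example (51% zeros, mean 4.98 days): Poisson 0.058/0.194 = 0.30; negative binomial 0.272/0.194 = 1.40; sandwich 0.199/0.194 = 1.03.

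Further hospital-day runs used 0.4 admissions a year with log-normal stays and frailty. Across them the negative binomial SE/SD was mostly 1.2-1.5 (extremes 1.12 and 1.56), with type I error 0-2.8%. At two corners of these assumptions (150 runs each, 14 and 19 dropped for unusable errors) the zero-inflated negative binomial gave 0.96 (type I error 5.9%) and 0.82 (12.2%). The second was the heavier-tailed case.

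**5. What fit would select.** Among the four families in step 4, AIC chose the zero-inflated negative binomial for hospital days in 900 of 900 runs. For ER visits it chose the negative binomial in 808 and its zero-inflated form in 92 of 900.

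**6. What that model tests.** With zero-inflation probability p and count mean m, the mean total is (1 - p) x m. The log ratio of mean totals is therefore the log ratio of (1 - p) plus the log ratio of m, and the count-part interaction is only the second term. An intervention that prevents admissions moves part of its effect into the zeros.

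For a 35% cut in admissions with stay length unchanged, the true log ratio is ln(0.65) = -0.43. In 200 runs per scenario:
- The count-part interaction averaged -0.12 to -0.25. Since exp(-0.12) = 0.89 and exp(-0.25) = 0.78, it would read as an 11-22% reduction.
- Its power was 10-25%. The log ratio of mean totals with a sandwich error had power 32-48%, with type I error 3.5-5.0%.

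A separate set of 240 runs (median stay 5.5 days, log-SD 0.9) gave -0.17 with a constant zero part and -0.13 with a full zero part. Power was 14% and 10% respectively, against 31% for the sandwich test and 9% for the plain negative binomial.

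**The case against.** The strongest reply is that the plan already allows for excess zeros and picks by fit, so a poorly fitting Poisson or plain negative binomial would not survive. On standard-error size that largely stands: the family AIC selects is about right, or too narrow with heavy tails. It does not rescue the tested quantity (step 6), and with no named criterion, selection by AIC is itself an assumption.

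A reader might infer a fixed direction: errors too wide for hospital days and too narrow for ER visits. The documents do not support this. Too wide arises only under the plain negative binomial; Poisson errs the other way. For ER visits, one set of runs with log-normal heterogeneity gave negative binomial errors 4-20% too small (type I error 7-13%). The runs in step 4 gave ratios on both sides of 1, and in the heavy-tailed scenario the sandwich test also reached 9%.

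Three further objections stand as limits:
- That the error is model-based is inferred from the plan's silence, though it is the usual default for a likelihood GLMM.
- The plan also carries a random time effect. Adding a participant-by-period effect to the Poisson model (100 runs) brought ER SE/SD to 1.13 and 0.97. For hospital days that fit was unstable and is not relied on.
- Eligibility can select on an ER visit or hospitalisation in the past year, which shapes the pre-period totals. The scenarios described do not mention this.

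**Conclusion.** The point holds for hospital days and is not shown for ER visits. Across the permitted families the random-intercept standard error ranged from about a fifth of the true spread to roughly one and a half times it. The family most likely to be chosen on fit has a roughly correct error (SE/SD 0.82-1.03) but recovers only about 28% (0.12/0.43) to 58% (0.25/0.43) of the log reduction in total days.

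The power gap between that model and the sandwich test is not explained by an undersized test, because the zero-inflated model's type I error was at or above nominal in most runs. The plain negative binomial comparison is less clean, since its low power partly reflects its very small type I error.

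The sizes are illustrative: rates, stay lengths, frailty and the 35% effect are all assumed, and the scenario has the intervention acting on admissions rather than on length of stay. If inverse probability weighting is used, a model-based error is in further doubt. This is a cheap improvement worth making, not a defect that invalidates Aim 3.

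**What to change.** Add to the Aim 3 (1) analysis: *The tested quantity for each outcome is the arm-by-time log ratio of mean 12-month totals from a log-link mean model. Tests and intervals use a participant-level robust (sandwich) standard error, or a re-randomisation test within the diagnosis-by-age randomisation strata, whatever working distribution is fitted. Zero-inflated models are supportive.* State this before unblinding. If weighting is kept, the robust error or the re-randomisation should cover the weighting step too.

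The cost is a short SAP addition and an option in standard software. The sandwich test can be mildly liberal with very heavy tails (up to about 9% in one ER scenario), so the re-randomisation version is preferable there. It takes somewhat more work, because an interval has to be obtained by inverting the test.

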The proposed study will randomize people with serious mental illness to I-IMR (n=300) and CDSMP (n=300) to address the following four specific aims and hypotheses:

Aim 1: Compare the effectiveness of I-IMR to CDSMP with respect to our primary ***physical health self-management outcomes***.

Hypothesis 1: I-IMR compared to CDSMP will be associated with greater improvements in ***physical health self-management abilities*** (Self-Rated Abilities for Health Practices scale; SRAHP, and a qualitative interview) and ***physical health consumer activation*** (Patient Activation Measure; PAM); and (secondary hypothesis) greater improvement in self-reported ***physical health*** functioning (PROMIS Global Health measure).

Aim 2: Compare the effectiveness of I-IMR to CDSMP with respect to our primary ***mental health self-management outcomes***.

Hypothesis 2: I-IMR compared to CDSMP will be associated with greater improvements in ***mental health self-management abilities*** (Illness Management and Recovery Scale; IMRS, and a qualitative interview); and ***mental health consumer activation*** (PAM-MH); and (secondary hypothesis) greater improvement in self-reported ***mental health*** (PROMIS Global Health measure).

Aim 3: Compare the effectiveness of I-IMR to CDSMP with respect to ***emergency room and acute care hospital days***, and risk of ***10-year cardiovascular mortality***.

Hypothesis 3: Participation in I-IMR compared to CDSMP will be associated with fewer emergency room admissions and acute care hospital days over 12 months compared to the 12 months before participation; and greater reduction in 10-year cardiovascular risk score (ACC/AHA Cardiovascular Risk Score) from baseline to 12 months.

Aim 4: Compare I-IMR to CDSMP with respect to subgroup differences in self-management outcomes by **mental illness subgroup** (schizophrenia-spectrum vs. mood disorders) and by **age group** (18-49 vs. 50+).

Hypothesis 4: Comparing I-IMR and CDSMP, the difference in treatment effects will be greater for people with schizophrenia spectrum disorders compared to mood disorders; and greater for older (age 50+) compared to younger (18-49) participants with respect to: **physical health self-management abilities and activation** (SRAHP; PAM); **mental health self-management abilities and activation** (IMRS; PAM-MH); and 10-year ***cardiovascular risk reduction*** (ACC/AHA Cardiovascular Risk Score).

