COVID-19 Enhancement Primary Aim: After co-design of the 3-session I-IMR module, we will evaluate the impact of the module by comparing participants assigned to I-IMR (n=75) to participants assigned to CDSMP (n=75) on the primary and secondary outcomes (**primary**: knowledge and use of measures to prevent contracting and spreading COVID-19; **secondary**: use of healthcare services for COVID-related concerns; perceived isolation and social disconnectedness).

Primary Hypothesis: I-IMR participants will demonstrate greater improvements in their scores on the primary outcome measure (a measure of knowledge and behaviors to prevent contracting and spreading COVID-19 developed for this project) compared to CDSMP participants.

Secondary Hypothesis: I-IMR compared to CDSMP participants will demonstrate less COVID-related health care service use and greater improvements in social connectedness.

Exploratory Aim: Explore differential response with respect to race/ethnicity (Black versus White adults); age (older versus younger adults); and psychiatric diagnosis (schizophrenia-spectrum vs. mood disorders).

Exploratory Hypothesis: Effect sizes for the I-IMR module versus generic support calls alone will be even greater among Blacks v. Whites, older (55+) v. younger adults, and people with schizophrenia-spectrum v. mood disorders.

3. Study Design

The proposed study is to compare I-IMR and CDSMP in improving outcomes of importance to the target population of people with SMI: optimizing personal physical and mental health, being an active agent in determining personal physical and mental health wellness goals, decreasing risk of early mortality, and minimizing use of the ER and hospitals. A secondary objective is to learn whether psychiatric diagnosis and/or age interacts with treatment, specifically, whether treatment effects vary more for participants with schizophrenia or older age. Consistent with a truly pragmatic trial, inclusion criteria are broad and exclusion criteria are limited. Participants will be randomized, stratified by diagnosis (schizophrenia spectrum vs. mood disorder) and age group (age 18-49 vs. age 50+).

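### For ER visits and hospital days, a count of tested baseline imbalances should not choose between covariate adjustment and inverse probability weighting (minor)

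*Combined protocol and SAP*

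**What the plan says.** In the combined protocol and SAP, section 4, Analysis for Aim 3, ER visits and hospital days are totalled for a year before and a year after, and fitted with a log-link mixed model (GLMM). The terms are: "The arm, time (before vs. after) and arm*time interaction will be included as fixed effects". The interaction tests superiority. This serves Hypothesis 3 in section 2, which expects "fewer emergency room admissions and acute care hospital days over 12 months compared to the 12 months before participation".

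The plan then adds a balance step: "For this analysis, because we cannot ensure covariates are balanced between two arms 12-months before randomization, we will test group (arm) balance" on demographic and clinical variables. The next sentence gives the consequence: "Depending on the number of imbalances we find, we will either include covariates in the model or use propensity score adjustment", the latter by inverse probability weighting. The count distribution (Poisson, negative binomial or zero-inflated) is left to model fit.

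Three other places bear on this:

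- Section 3, Study Design: "Participants will be randomized, stratified by diagnosis (schizophrenia spectrum vs. mood disorder) and age group (age 18-49 vs. age 50" and over).
- Section 4, Evaluation of Attrition: 600 participants, 300 per arm. "Based on previous experience, we assumed 20% attrition by 12 months".
- Section 4, Analysis for Aim 1: the analysis is intention-to-treat on the full sample, and the terms are fixed with no branching. "Treatment arm (I-IMR and vs. CDSMP), time (baseline, 4-, 8- and 12-month), and arm-by-time interactions will be specified as fixed effects". The two randomisation strata are not among them.

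The supplied text does not list the variables tested, the test or its level, the number of imbalances that separates the branches, the contents of the propensity model, or who makes the choice and when. The heading Evaluation of Group Equivalence is followed only by subgroup and multiplicity text, so material there may have been lost. References 103 and 104, on ANCOVA and covariate adjustment, are listed but not cited in the supplied text.

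**The concern.** The reason given for the balance step is that balance in the year before randomisation cannot be assured. But that year belongs to the same people who were then randomised. For variables fixed before randomisation, in all 600, the null hypothesis of a balance test is true by design. A significant result shows only that chance has operated, and a count of such results says nothing about which estimator is better.

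The rule also leaves the analysis undetermined. There are two named branches, plus an implied unadjusted one if no imbalance is found. Two analysts could follow the text faithfully and report different estimators for the same named hypothesis.

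The branches do not do the same job. A main effect of a variable that is constant over time does little to an arm-by-period contrast, whereas weighting does move it.

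**Working it through.** **1. The plan's own figure.** 600 × (1 − 0.20) = 480, which matches section 9, item b. It is the only sample-size figure that covers Aim 3. The documents give no event rate, effect size or power for that aim.

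**2. How often the trigger would fire.** With *k* independent variables each tested at level α, P(at least *r* imbalances) = 1 − Σ C(k, j) α^j (1 − α)^(k−j), summed over j < r. For r = 1 and α = 0.05 this is 1 − 0.95^k: 1 − 0.774 = 0.226 (k = 5), 1 − 0.599 = 0.401 (k = 10), 1 − 0.358 = 0.642 (k = 20). Both k and α are assumptions, because the plan states neither.

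| k | α | at least 1 | at least 2 | at least 3 |
|---|---|---|---|---|
| 5 | 0.05 | 22.6% | 2.3% | 0.1% |
| 10 | 0.05 | 40.1% | 8.6% | 1.2% |
| 20 | 0.05 | 64.2% | 26.4% | 7.5% |
| 20 | 0.10 | 87.8% | 60.8% | 32.3% |

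If IPW is used once *r* imbalances appear, its probability runs from about 0.1% to about 88%, depending on three numbers that the supplied text does not give.

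**3. What the choice does to the result.** Two null simulations were run, with all rates assumed.

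*Simulation A.* The design had 600 participants, blocks of 4 within diagnosis-by-age strata, and overdispersed counts with means 1.5 before and 1.3 after. After-period counts were complete or about 20% missing. There were 10 or 20 covariates, half of them prognostic, and only imbalanced ones entered either branch. Models were Poisson or negative-binomial estimating equations with cluster-robust standard errors, in 12 settings of 8,000 trials. In trials with at least one imbalance:

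- Covariate main effects moved the arm-by-period estimate by a median of 0.00 to 0.05 SE; IPW moved it by 0.07 to 0.08 SE.
- The branches differed by a median of 0.07 to 0.10 SE (95th percentile 0.22 to 0.37).
- They disagreed on significance in 0.8% to 1.8% of these trials, or 0.3% to 1.2% of all trials.

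Type I error across settings was 0.0476 to 0.0574 unadjusted. It was 0.0475 to 0.0583 under a fixed rule (0 imbalances unadjusted, 1 or 2 covariates, 3 or more IPW; assumed), a change of at most 0.001. Taking the smaller p-value gave 0.0510 to 0.0631, an addition of 0.002 to 0.007.

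A check with random-intercept GLMMs gave a median branch difference of 0.07 to 0.11 SE. The Poisson values there are overstated, because the model SE was 0.096 against an empirical SD of 0.136. Zero-inflated models were not simulated.

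*Simulation B.* This used 10 covariates, all of them in both branches, 2,000 trials per setting and a Poisson model with clustered SE. The two rate ratios differed by a median of about 2% and by 6% to 8% at the 95th percentile. The branches disagreed on significance in about 1.6% of trials. Rejection if either branch could be reported was 6.1% against 5.1% to 5.4% for each alone (240 per arm), and 7.2% against 6.2% to 6.5% (300 per arm). That is an addition of about 0.007 to 0.010.

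**4. Strata left out of the models.** Suppose the strata explain a share R² of the variance in slope or change, and power would be 80% with them included. Stratified randomisation already removes that share from the sampling variance, but a model without the strata still counts it in its SE. Hence type I error = 2 × [1 − Φ(1.96/√(1 − R²))] and power = Φ(2.80 − 1.96/√(1 − R²)).

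| R² | type I error | power |
|---|---|---|
| 0.02 | 0.0477 | 0.794 |
| 0.05 | 0.0443 | 0.785 |
| 0.10 | 0.0388 | 0.769 |

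A simulation with 480 participants agreed: type I error was 0.0474, 0.0438 and 0.0390 with the strata omitted, and 0.0494, 0.0494 and 0.0507 with them included. The R² range and the 80% are assumptions; the documents state 80% power only for the COVID component.

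**The case against.** The strongest reply is that these numbers show almost nothing. A fixed rule moves type I error by no more than 0.001, less than the spread of the unadjusted model across settings. The rule looks at covariates, and a report can say which imbalances were found and which branch was used. Lost text might hold the list and the cut-off. Leaving out the strata is a matter of preference. All of this bears on severity and supports calling the point minor. It does not rescue the rule: a list and a cut-off would make the choice reproducible, but would still let chance imbalance select the estimator.

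The reply also limits the word chance, and that limit stands. The Aim 3 text counts events before and after the intervention, yet justifies the balance step by the year before randomisation, and Hypothesis 3 speaks of participation. A window anchored to intervention start could extend past allocation. With 20% attrition, the people who have after-period counts need not be balanced by design. The argument therefore covers variables fixed before randomisation in all 600, and no more.

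Two stronger readings are tempting. A reader might infer that the estimator can be chosen after seeing the treatment effect. The text does not say that after-period results are consulted. The before-period counts are half of the modelled outcome and the timing of the choice is unstated, but that is silence and not permission. A reader might also infer a threat to the primary results. Section 2 attaches the label primary to Aim 1 and 2 outcomes, and the fixed effects of those models contain no such branch.

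**Conclusion.** The point holds as a minor one, confined to ER visits and hospital days. A data-driven rule with no valid statistical basis chooses the estimator, and as supplied it does not settle the estimator before baseline data are examined. The cost is mainly to transparency; no large bias is shown. The type I error change is at most about 0.001 under a fixed rule and up to about 0.01 under favourable picking. Both figures rest on assumed event rates, covariate effects and counting rules, and mostly on estimating equations in place of the planned GLMM.

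A reader might infer that leaving the strata out biases the Aim 1 to 3 models. It does not. It makes the arm-by-time test slightly conservative: type I error 0.048 to 0.039 and power 79% to 77% instead of 80%, if R² is 2% to 10%.

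**What to change.** Delete the balance-test and weighting rule. Suggested replacement:

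> ER visits and hospital days will be analysed with one primary GLMM containing arm, period, arm-by-period, diagnosis stratum, age stratum and each stratum-by-period term, using the strata recorded at randomisation. Before and after windows are counted from [one stated date]. The count distribution is [named here], or is chosen by [stated criterion] from fits without arm terms. Baseline balance will be described, not tested, and will not change the model. IPW, with its covariates listed here, is a sensitivity analysis only.

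The distribution clause is needed because, without it, the analysis would still not be fixed in advance. For the window, the randomisation date is the choice that keeps the before period wholly ahead of allocation.

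Add the two strata and their interactions with time to the other Aim 1 to 3 models as well.

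The cost is SAP wording, plus 4 parameters with before/after or linear time (2 main effects + 2 interactions), or 8 with four categorical visits (2 + 2 × 3), among 480 to 600 participants. In Simulation A, the strata model changed the SD of the arm-by-period estimate by less than 1% and kept type I error within about 0.003 of the unadjusted model. For these counts, then, the gain is a fixed analysis and not precision. In the other models there is no gain if the strata do not predict change.

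### Aim 3(1): covariates entered only as main effects leave the tested arm-by-time term unchanged or nearly so, so the covariate branch does not remove imbalance in covariates that predict change

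*Combined protocol and SAP*

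**What the plan says.** Section 4, Analysis for Aim 3, totals each person's ER visits and hospital days over the 12 months before and the 12 months after, and reuses the Aim 1 mixed model with a "log link function and Poisson, or negative binomial or zero-inflated distribution (depending on model fit"). On the model terms: "The arm, time (before vs. after) and arm*time interaction will be included as fixed effects". On the test: the "superiority hypothesis of I-IMR compared to CDSMP will be tested with the significance of the interaction term".

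The plan then notes that balance in the period before randomisation cannot be ensured. Its response has two steps. First, "we will test group (arm) balance with respect to demographic and clinical covariates". Second, depending on how many imbalances appear, "we will either include covariates in the model or use propensity score adjustment with inverse probability weighting to balance the groups". It does not give the number that decides between the branches, the covariate list, or the form in which covariates enter.

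Two other statements bear on the model. Analysis for Aim 1, whose model is reused here, says "Intercept and time will be specified as random effects". Evaluation of Attrition assumes 20% loss by 12 months.

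**The concern.** The test is a difference between arms in before-to-after change. An imbalanced covariate can distort it only if the covariate also predicts change. Adding that covariate as a main effect says that it raises or lowers a person's rate by the same factor in both years, and such a factor drops out of a before/after ratio. The model then fits the level of use better but says nothing new about change.

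Main effects are the natural reading because the fixed effects listed for Aim 3 contain no covariate-by-time term, and the plan writes interactions out where it wants them, as with the three-way term in Analysis for Aim 4.

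At stake is how the ER and hospital-day result is read. If the covariate branch is triggered, the report would show a covariate-adjusted result that is essentially the unadjusted one, while the other branch would give a different estimate. Naming the covariates in advance would not cure this if they still entered only as main effects.

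**Working it through.** The documents give no effect size, power or alpha for Aim 3(1), so there is no planned figure to reproduce. The check is algebra, followed by simulation under assumed inputs.

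**1. Algebra (Poisson, random intercept, complete pairs).** For person i in arm a (0 or 1), at time t (0 before, 1 after), with covariate x:

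log mean = α + β·a + τ·t + δ·a·t + γ·x + u, where u is the random intercept and δ is the tested term.

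- Given the person's two-year total, the after-count is binomial with logit(p) = τ + δ·a. The terms α, β, γ·x and u cancel.
- The total has mean exp(α + β·a + γ·x + u) × [1 + exp(τ + δ·a)]. The bracket takes one value per arm, so the free α and β absorb it.
- The likelihood therefore splits into a part for totals (with γ and the variance of u) and a part for the split (with τ and δ). The estimate is δ = log(after total / before total) in I-IMR minus the same in CDSMP. The covariate does not appear.
- With covariate-by-time added, logit(p) = τ + δ·a + θ·x, and δ is now adjusted for x. With weighting, the totals become weighted totals, and δ also changes.

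**2. Expected bias.** Approximately imbalance × covariate effect on log change. Two sets of assumed inputs were used, neither from the documents:

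- Set A: n = 600, continuous covariate, imbalance 0.3 SD, effect on change 0.3. Bias ≈ 0.3 × 0.3 = 0.09.
- Set B: n = 480 (600 × 0.80), binary covariate, 10-point imbalance, effect on change -0.4. Bias ≈ 0.10 × (-0.4) = -0.04.

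**3. Mean arm-by-time estimate, truth 0.**

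| Model and data | Unadjusted | Main effect | Covariate-by-time | Weighting |
|---|---|---|---|---|
| A: Poisson without random effects, complete pairs, 60 data sets | 0.084 | 0.084 | -0.008 | -0.004 |
| A: Poisson random intercept, 20% dropout, 60 data sets | 0.097 | 0.094 | not run | not run |
| A: negative binomial random intercept, complete pairs, 60 data sets | 0.058 | 0.062 | not run | -0.025 |
| B: Poisson, random intercept and time, 10 data sets | -0.054 | -0.052 | -0.004 | not run |
| B: zero-inflated version, 10 data sets | -0.053 | -0.062 | -0.026 | not run |

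The last two rows rest on few data sets. With a standard error near 0.12, the Monte Carlo error of a mean is about 0.12/√10 ≈ 0.04. Compare the columns within a row, which come from the same data, rather than the levels.

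**4. Shift within a data set when the main effect is added.**

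- Poisson, complete pairs: none. In one Set A data set the estimate was 0.317839 with and without the covariate, against 0.180 with covariate-by-time and 0.226 with weighting (random-intercept fits). The largest difference over 60 data sets, in fits without random effects, was about 1e-14.
- Poisson random intercept, 20% dropout: mean 0.007, maximum 0.031.
- Negative binomial random intercept: at most 0.008 in 40 data sets (Set B) and at most 0.014 in a separate check; mean 0.019, maximum 0.060 in 60 data sets (Set A).
- Poisson with random intercept and random time: mean 0.016, maximum 0.045 in 15 data sets with Set B's imbalance and effect on change; standard error about 0.12.

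**5. Scale.** Under Set B, covariate-by-time moved the estimate by 0.036 on average and by up to 0.088. The standard error of arm-by-time in similar data was 0.11 to 0.15. So 0.036/0.15 = 0.24 and 0.036/0.11 = 0.33, roughly a quarter to a third of a standard error.

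**The case against.** The strongest reply has four parts.

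- **Exact invariance belongs to a model the plan may not fit.** It needs Poisson counts, a random intercept only, and complete pairs. The plan expects skewed counts with many zeros, allows negative binomial and zero-inflated models, carries over a random time effect and expects 20% attrition. This stands: in those settings the term moves. But the movement is small and does not remove the bias. A negative binomial fit without random effects moved further in one data set (-0.028 to 0.115), but the plan specifies a mixed model.
- **The plan never says main effects only.** This also stands. Main-effect entry is the natural reading, but it is an inference, and nothing in the text excludes covariate-by-time. That silence is what the fix addresses.
- **The plan has a second branch.** A reader might infer that the whole imbalance step adjusts nothing. The documents do not support that: inverse probability weighting changes arm-by-time and, in the Poisson simulations, took the bias from 0.084 to -0.004.
- **Randomisation makes any imbalance a chance one.** A reader might infer that the Aim 3(1) test is invalid. It is not: allocation is random and stratified by diagnosis and age group, so the unadjusted test is valid on average. The gain from proper adjustment is correspondingly modest.

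**Conclusion.** The covariate branch of Aim 3(1), read as main effects, does not do the job the plan gives it. The tested term stays exactly the same in a Poisson random-intercept model with complete pairs. In the other models and data conditions the plan allows, it changes slightly, with most of the imbalance bias left in place. The weighting branch does change the term, so the two branches are not interchangeable, and the choice between them rests on an unstated count of imbalances.

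The algebraic result needs no assumed numbers. All sizes of shift and bias are illustrative, because the imbalance and the covariate's effect on change are assumed. Where a covariate is balanced, or does not predict change, the point has no practical effect on the estimate. It is worth correcting because this is the plan's own safeguard for the utilisation hypothesis and the correction is cheap.

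**What to change.** In Analysis for Aim 3, replace the open-ended reference to including covariates with a rule such as: covariates enter with both their main effect and their interaction with time; the set is the stratification factors (diagnosis and age group) plus a named list fixed before unblinding; a covariate entered only as a main effect does not count as adjustment of the arm-by-time test.

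An acceptable alternative is to model the post-year count with arm, the pre-year count and the same covariates as predictors, and to test the arm effect. There, covariate main effects do adjust the tested term.

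The cost is a sentence or two in the analysis plan and a few extra model parameters. No new data are needed.
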